
Exercise sub-study:
 
To determine whether famotidine increases maximal oxygen uptake in individuals with pulmonary arterial hypertension at 24 weeks
 
To explore changes in other metrics of the exercise response (oxygen uptake, V_e/V_{CO_2} ratio, total achieved wattage) with famotidine relative to placebo over 24 weeks.
 
Right heart catheterization sub-study:
 
To determine whether famotidine increases stroke volume index at 24 weeks
 
To explore whether famotidine is associated with differences in wedge pressure, right atrial pressure, and/or pulmonary vascular resistance at 24 weeks
	
The primary analyses will be the change in oxygen consumption (VO_2) for the exercise sub-study and the change in stroke volume index (SVi) for the right heart catheterization sub-study conducted using the intent-to-treat (ITT) population.
 
Qualitative descriptions of other exercise and hemodynamic markers including mean, median, and distribution will be presented stratified by treatment group.
	
While the two proposed sub-studies are powered to detect plausible, but large differences in exercise response or invasive hemodynamic markers, these studies are not powered to detect small to moderate differences. The co-primary intent of these sub-studies is to begin to understand appropriate end-points in trials of right heart targeted therapy. This more exploratory motivation is intended to complement but not supplant primary and secondary outcome measures.

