and pregnancy test if indicated. The pregnancy test can be performed as either a blood or urine test. A blood-based pregnancy test is preferred; however, if a urine test is used then it must be performed by study personnel and documented in the medical record. All participants will have serum collected for mass-spectrometry at the end of the study to evaluate for contamination of the study question by individuals taking over-the-counter H2 receptor antagonists. Serum, plasma, and blood for RNA isolation will be collected and stored for participants.

Adverse events and concomitant medications will be assessed and collected at all visits.

Optional Right Heart Catheterization (RHC) Evaluation: Subjects will have the option to take part in the RHC portion of the study that will be performed within 14 days of the Baseline Visit and within 7 days of the Week 24 Visit. The baseline visit must be done while not taking study drug and the week 24 visit must be done while taking study drug. This is a procedure which is performed for all patients with PAH. The purpose of this optional evaluation is to track changes in the measurements of the subjects' heart and lungs that might be related to study treatment with famotidine. 1% lidocaine local anesthesia will be used. It will take 3-4 hours to complete the right heart catheterization. On the day of the right heart catheterization, subjects will check into the cardiac catheterization laboratory at the University of Washington Medical Center. A nurse will check the subject's vital signs and basic bloodwork to make sure that the procedure is safe to perform. Once this is done, subjects will go into the cardiac catheterization laboratory where [name] will numb the area for the procedure with lidocaine. This will typically be the right side of the neck. After numbing the area, [name] will place a catheter into a vein, the right atria, right ventricle, and pulmonary artery and measure pressures at each position and check to see how much blood the heart is pumping. The process of inserting the catheter and taking measurements normally takes approximately 20-30 minutes. After these measurements, the catheter will be removed, a nurse will hold pressure on the area to ensure that there is no bleeding, and the subject will then be free to go.

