Optional Cardiopulmonary Exercise Test (CPET) Evaluation: Subjects will have the option to take part in the CPET portion of the study that will be performed within 14 days of the Baseline Visit and within 7 days of the Week 24 Visit. The baseline visit must be done while not taking study drug and the week 24 visit must be done while taking study drug. CPET will be done via bicycle ergometry and will be performed in the Exercise Testing Laboratory of the UW Lung Function Testing Center. This is a routine clinical test used by pulmonologists and cardiologists, but is not routinely done for all individuals with PAH. This test measures how the body tolerates physical activity. Due to the Covid 19 Pandemic, the Lung Function Testing department at UWMC is requiring Covid testing prior to any procedures done in the lab. As long as this requirement is in place, you will be given a phone number to call to arrange testing at a drive through testing site within 72 hours of your appointment. At the drive through site, you will stay in your car and a nurse will use a nasal swab (like a long Q-tip) inserted into your nose and back of throat to collect cells which will be sent to the lab. You will be notified in the event of a positive test result.

On the day of the test, subjects will check into the Lung Function Testing Center at the University of Washington Medical Center. They should wear clothing suitable for exercise. A respiratory therapist will

check the subject's vital signs and conduct breathing tests. After this they will hook up an EKG, monitor the subject's oxygen via a probe on their finger, and place a neoprene mask over their nose and mouth. These will measure a number of important exercise characteristics. Subjects will then ride a stationary bicycle in the exercise lab. The test is variable in length and designed to push the subject to exercise as hard as they can tolerate in a highly supervised setting. Most participants exercise for 5-15 minutes with increasing resistance on the stationary bicycle. This is followed by a "cool-down" period on the bicycle. When the subject is done, a respiratory therapist will continue to monitor the subject for 5-10 minutes at rest. After this time, subjects will be free to go.

Participants in the invasive hemodynamic and cardiopulmonary exercise testing (CPET) sub-studies will have the option to do both tests on the same day or separate days, but within the 3 days of the final visit.

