9.3 POPULATIONS FOR ANALYSES

Intent-to-Treat Population: All subjects who are randomized will comprise the intent-to-treat (ITT) population. The ITT population will be analyzed for the primary and secondary endpoint analyses and will comprise the safety population used for all safety analyses.

Per Protocol Population: Subjects in the ITT population whose famotidine medication reconciliation suggest adherence to study drug for 80% or more of administered doses will be evaluated as the per protocol population. The per-protocol population will be used in the sensitivity analyses of the primary and secondary endpoints. A second per protocol population will include participants for whom H₂ receptor antagonists are detected by Mass Spectrometry at the final visit relative to those for whom H₂ receptor antagonists are not detected.

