
Exercise sub-study:
 
To determine whether famotidine increases maximal oxygen uptake in individuals with pulmonary arterial hypertension at 24 weeks
 
To explore changes in other metrics of the exercise response (oxygen uptake, V_e/V_{CO_2} ratio, total achieved wattage) with famotidine relative to placebo over 24 weeks.
 
Right heart catheterization sub-study:
 
To determine whether famotidine increases stroke volume index at 24 weeks
 
To explore whether famotidine is associated with differences in wedge pressure, right atrial pressure, and/or pulmonary vascular resistance at 24 weeks
	
The primary analyses will be the change in oxygen consumption (VO_2) for the exercise sub-study and the change in stroke volume index (SVi) for the right heart catheterization sub-study conducted using the FAS.
 
Qualitative descriptions of other exercise and hemodynamic markers including mean, median, and distribution will be presented stratified by treatment group.
	
While the two proposed sub-studies are powered to detect plausible, but large differences in exercise response or invasive hemodynamic markers, these studies are not powered to detect small to moderate differences. The co-primary intent of these sub-studies is to begin to understand appropriate end-points in trials of right heart targeted therapy. This more exploratory motivation is intended to complement but not supplant primary and secondary outcome measures.

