5.4 Withdrawals, Dropouts, Loss to Follow-up

Discontinued subjects will not be replaced whether they received or did not receive the study drug. The multiple imputation approach is included in Section 6.4.

Follow-up of subjects who discontinued the study drug early will continue until Week 24 and the study procedures will be assessed as per the schedule of assessment (see Table 9-1).

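### The Protocol's on-drug rule for the Week 24 catheterization and exercise tests conflicts with the SAP's follow-up of early stoppers and with the ITT/FAS label on the sub-study endpoints

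*Protocol*

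**What the plan says.** Protocol 8.1 has one paragraph for the right heart catheterization (RHC) sub-study and one for the cardiopulmonary exercise test (CPET) sub-study. Each gives a window around the Week 24 visit and then the same sentence: "The baseline visit must be done while not taking study drug and the week 24 visit must be done while taking study drug". Neither paragraph mentions participants who stopped drug before Week 24.

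Protocol 3 has change in VO2 and change in stroke volume index "conducted using the intent-to-treat (ITT) population". Protocol 9.3 defines that set: "All subjects who are randomized will comprise the intent-to-treat (ITT) population". SAP Table 3-1 has the same endpoints "conducted using the FAS", and SAP 4.1 defines the FAS as randomized participants with at least one dose.

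For those who stop drug early, SAP 5.4 continues follow-up to Week 24 and says "the study procedures will be assessed as per the schedule of assessment". The schedule it points to, SAP Table 9-1, lists RHC and CPET at Week 24 with no on-drug condition.

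**The concern.** The Protocol's rule on when the test is done and the SAP's rule on who is followed cannot both be applied to a participant who stopped drug but stayed in the study. A site that reads 8.1 literally omits the Week 24 test; a site that follows SAP 5.4 and Table 9-1 performs it. If tests are omitted, the values available for stroke volume index and VO2 come only from people still on drug at Week 24. That condition is determined after randomization and may differ by arm, yet the result would carry an ITT or FAS label.

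The sub-studies also aim to relate exercise markers to BNP, functional class, quality of life and escalation of therapy (Protocol 1.1). For stoppers who remain in the study, those other markers are still due at Week 24 while the sub-study value would be absent. The relationship would then be described in a selected group.

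**Working it through.** The point rests on text, so the passages come first.

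1. **Condition on the test.** Protocol 8.1: "the week 24 visit must be done while taking study drug", stated for RHC and for CPET, with no exception.
2. **Condition on the analysis set.** Protocol: all randomized (9.3). SAP: all randomized and dosed (4.1). Neither requires drug use at Week 24.
3. **Stopping drug while staying in the study is foreseen.** Protocol 9.4.4 tabulates permanent discontinuation with and without study withdrawal as separate categories. Protocol 5.5 has staff stress follow-up even for non-adherent participants.
4. **Follow-up of stoppers.** SAP 5.4 and Table 9-1 include both tests at Week 24.
5. **Handling of a missing test.** SAP 6.4.1 and 6.4.2 specify imputation for the primary and secondary endpoints. SAP 6.4.3 specifies none for the sub-studies, and SAP 6.2.6 rules out imputation of efficacy endpoints beyond what Section 6.4 describes. A skipped test therefore drops out with no stated handling.

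**The plan's power figures.** The documents give no SD for either sub-study endpoint, so the power tables cannot be reproduced from stated inputs. They can be checked for consistency with a two-sample t test, two-sided alpha 0.05, df = n1 + n2 − 2 and noncentrality d / (SD × √(1/n1 + 1/n2)).

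- RHC, SD 8.7 mL/m² (solved for, not stated), differences 20/15/10/5: 0.998/0.954/0.681/0.230 at 10 per arm (Protocol 9.2: 0.99/0.95/0.68/0.23), and 0.888/0.667/0.360/0.127 at 5 per arm (0.87/0.67/0.36/0.13).
- CPET, SD 3.0 mL/min/kg (solved for), differences 8/4/2 at 5 per arm: 0.957/0.458/0.154 (SAP 6.1: 0.96/0.46/0.15).

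**Illustrative loss of precision, using those SDs.**

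- RHC, difference 15: 0.954 at 10+10, 0.942 at 10+9, 0.929 at 9+9, 0.893 at 8+8.
- RHC, difference 10: 0.681, 0.655, 0.629 and 0.571 for the same splits.
- CPET, difference 4: 0.458 at 5+5, 0.404 at 5+4, 0.355 at 4+4.

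**Illustrative shift in an arm mean.** Removing one of n participants who lies s below the arm's other members raises the arm mean by s/n. Both values of s are assumptions.

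- RHC, n = 10, s = 10 to 20 mL/m²: 10/10 = 1 to 20/10 = 2 mL/m², against 5 for the difference the plan labels small.
- CPET, n = 5, s = 4 mL/min/kg: 4/5 = 0.8 mL/min/kg.

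**Chance that at least one sub-study participant is affected.** No discontinuation rate is given. If a proportion p stop drug, stay in the study and would otherwise be tested, the chance is 1 − (1 − p)^n. For an assumed p of 5% to 20%:

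- RHC, n = 20: 1 − 0.95^20 = 64% to 1 − 0.80^20 = 99%.
- CPET, n = 10: 1 − 0.95^10 = 40% to 1 − 0.80^10 = 89%.

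**Test windows.** Protocol 8.1 allows each test within 7 days of the Week 24 visit. The last sentence of the CPET text gives 3 days of the final visit for participants in the sub-studies. The latest Week 24 visit is Day 168 + 7 = 175, so the latest test is Day 175 + 7 = 182. Two bottles hold 2 × 91 = 182 tablets, which at one a day cover Days 0 to 181. Supply therefore reaches almost to the end of the window. The dosing text (Protocol 6.1.2) stops at 24 weeks, however, and the final tablet count and study termination fall at the Week 24 visit. No text says whether drug continues until a later test.

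**The case against.** The strongest reply is that the sentence is a timing rule. It directly follows the window sentence and pairs the Week 24 condition with a baseline condition: the baseline test before the first dose, the final test before dosing ends. Nothing in 8.1 tells the site to skip the test in someone who stopped. SAP 5.4 addresses early stoppers expressly, and Protocol 5.5 supports following them. A reader might infer from 8.1 that stoppers are barred from testing. The documents do not establish that. What stands is that the sentence is an unqualified requirement, and that the Protocol and SAP give different answers if it is read as written.

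Other limits also stand:

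- A reader might assume that every affected participant still supplies a Week 24 walk distance. Protocol 7.1 lets the investigator withdraw participants for deterioration or inability to stay on drug, so some stoppers may have no Week 24 data at all.
- A reader might infer that on-drug testing is impossible after the Week 24 visit. The tablet supply does not support that; what is missing is an instruction. The 3-day sentence may apply only to participants having both tests.
- An on-drug measurement is a legitimate choice for a mechanistic sub-study, provided it is labelled as one.
- Protocol 9.4.4 expects drug discontinuation to be infrequent, the sub-studies are exploratory, and SAP 6.4.3 plans only summary statistics.

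**Conclusion.** The stated rules contradict one another. Protocol 8.1 as worded cannot be applied together with SAP 5.4 and Table 9-1, and literal use of it produces an on-drug summary under an ITT or FAS label with no handling of the missing tests. Whether that was intended cannot be settled from the documents.

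The consequence is limited to two optional, exploratory sub-studies that are summarised descriptively. The primary 6MWD endpoint carries no such condition and is unaffected. The size of any distortion is unknown: the shifts of 1 to 2 mL/m² and 0.8 mL/min/kg, the 5% to 20% stopping range and both SDs are assumptions or back-solved values, and they should not be read as estimates. With 10 and 5 participants per arm (if balanced), one omitted test is 10% or 20% of an arm. That justifies settling the wording before the data are summarised.

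**What to change.** Reconcile the two Protocol 8.1 sub-study paragraphs with SAP 5.4 and Table 9-1, and with the population named in Protocol 3 and SAP Table 3-1. Either route resolves the contradiction:

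- **If 8.1 is only a timing rule for participants still on drug,** say so. Week 24 sub-study data from willing participants who stopped then fall under SAP 5.4 and enter the FAS, with the on-drug subset as a sensitivity summary.
- **If on-drug testing is intended,** label the sub-study analysis as on-treatment in both documents, in place of ITT/FAS, and report the number excluded in each arm.

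In either case, record on/off-drug status and last dose date at each Week 24 test. Reconcile the 7-day and 3-day windows with each other and with the end of dosing. The choice between the routes is the sponsor's. This point does not ask for catheterization off drug, and Protocol 2.3.1 notes that the procedure carries a small risk of serious complications.

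The cost is wording in both documents and a small addition to the case report form. If off-drug tests are included, the observed drug effect may be slightly diluted; the on-drug summary would show by how much.

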8.2 ADVERSE EVENTS AND SERIOUS ADVERSE EVENTS

8.2.1 DEFINITION OF ADVERSE EVENTS (AE)

Any unfavorable and unintended sign (including an abnormal laboratory finding), symptom or disease temporally associated with the use of a medical treatment or procedure, regardless of whether it is considered related to the medical treatment or procedure.

8.2.2 DEFINITION OF SERIOUS ADVERSE EVENTS (SAE)

Any AE that results in any of the following outcomes:

- Death
- Life-threatening
- Event requiring inpatient hospitalization or prolongation of existing hospitalization
- Persistent or significant disability/incapacity

8.2.3 CLASSIFICATION OF AN ADVERSE EVENT

8.2.3.1 SEVERITY OF EVENT

AEs are graded according to the following scale:

Mild: An experience that is transient, & requires no special treatment or intervention. The experience does not generally interfere with usual daily activities. This includes transient laboratory test alterations.

Moderate: An experience that is alleviated with simple therapeutic treatments. The experience impacts usual daily activities. Includes laboratory test alterations indicating injury, but without long-term risk.

Severe: An experience that requires therapeutic intervention. The experience interrupts usual daily activities. If hospitalization (or prolongation of hospitalization) is required for treatment it becomes an SAE.

8.2.3.2 RELATIONSHIP TO STUDY INTERVENTION

The study uses the following AE attribution scale:

Definite: AE is clearly related to study drug or a study procedure

Probable: AE is likely related to study drug or a study procedure

Possible: AE is possibly related to study drug or a study procedure

Unlikely: AE is doubtfully related to study drug or a study procedure

Unrelated: AE is clearly not related to study drug or a study procedure

8.2.3.3 EXPECTEDNESS

Expected AEs associated with famotidine include:

Headaches

Although expected AEs associated with right heart catheterization are uncommon, they include: Pain/discomfort, nausea, vomiting, redness, irritation, bruising, or development of a small hematoma/bleeding, allergic reactions in rare instances (e.g. hives or difficulty breathing from lidocaine or catheters), infection, damage to nearby structures (artery, vein, nerve, lung), hypertensive crisis, hypotension, chest pain, bronchospasm, arrhythmia, dizziness/syncope, or death (Hoeper et al., Complications of right heart catheterization procedures in patients with pulmonary hypertension in experienced centers, J Am Coll Cardiol; 48: 2546-52, 2006).

Although expected AEs associated with exercise testing are uncommon, they include: Changes in blood pressure and heart rate, fatigue, discomfort, musculoskeletal injury, syncope, arrhythmia, heart attack, or stroke (Skalski et al. The safety of cardiopulmonary exercise testing in a population with high-risk cardiovascular diseases, Circulation; 126:2465-72, 2012).

Expected AEs associated with the underlying natural history of pulmonary arterial hypertension or PAH therapies over a 24-week study include:

Dizziness, syncope, leg swelling, abdominal swelling, chest pain, shortness of breath, hypoxemia, hemoptysis, nausea, vomiting, diarrhea, jaw pain, flushing, joint pain, muscle pain, infection, arrhythmia, heart failure, pericardial effusion/tamponade, cirrhosis, thrombosis or embolus, stroke, cardiac arrest, or sudden cardiac death.

8.2.4 TIME PERIOD AND FREQUENCY FOR EVENT ASSESSMENT AND FOLLOW-UP

The study team will record all reportable events with start dates occurring any time after informed consent is obtained until 7 (for non-serious AEs) or 14 days (for SAEs) after the last day of study participation. AEs are identified at any of the three in-person visits, during a phone visit, during a study-based procedure (e.g. heart catheterization or cardiopulmonary exercise test) or when notified outside of the normal visit structure by a participant or surrogate. Events will be followed until resolution or stabilization.

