5.2 Data Conventions

The following conventions will be used:

- **Period definition:**
 - **Screening Period:** The period prior to the date of first dose of study drug (Day 0)
 - **On-Treatment Period:** The period from date of first dose of study drug through the Week 24 study visit
- **Study day 0:** The date of first dose of study drug
- **End of Treatment Visit:** End of treatment/early withdrawal visit
- **End of Study Visit:** The last recorded visit date
- **Unscheduled or repeated visits:** Unscheduled visits results will be listed, but not included in tables or graphs.
- **Conversion factors:**
 - 1 month = 30.4375 days
 - 1 year = 365.25 days
 - 1 week = 7 days
 - °C = (°F - 32)/1.8
- **Additional rules**
 - Age (years) = (date of informed consent – date of birth + 1) / 365.25, rounded to the lowest whole number.
 - Weight values recorded in pounds will be converted to kilograms using the following formula: kilograms = pounds/2.2046.
 - Height values recorded in inches will be converted to centimeters using the following formula: centimeters = inches*2.54.

- Duration on study (weeks) = (Last visit date – randomization date + 1) / 7.
- Duration on treatment (weeks) = (Last study drug intake date – first study drug intake date + 1) / 7.
- (Absolute) Change from baseline = Value at the time point – Baseline value.
- Relative change from baseline = [(Value at the time point – Baseline value) / Baseline value] x 100.

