6.6.1 Adverse Events

Adverse events (AEs) will be coded using the Medical Dictionary for Regulatory Activities (MedDRA), see Section 5.1, and displayed in tables and listings using System/Organ/Class (SOC) and Preferred Term (PT).

Analyses of adverse events will be performed for those events that are considered treatment emergent, where treatment emergent is defined as any adverse event with onset after the administration of study medication through the end of the study (see Section 5.2) or any event that was present at baseline but worsened in intensity or was subsequently considered drug-related by the investigator through the end of the study.

Adverse events are summarized by subject, therefore, in any tabulation, a subject contributes only once to the count for a given adverse event (SOC or preferred term).

The number and percentage of subjects with any treatment-emergent adverse event (TEAE), any treatment-emergent adverse event by severity, with any treatment-emergent adverse event by relationship to study drug, with any treatment-emergent adverse event leading to withdrawal from study drug, and with any treatment-emergent serious adverse event (SAE) will be summarized by treatment group and overall. In these tabulations, each subject will contribute only once (i.e., the most related occurrence or the most intense occurrence), regardless of the number of episodes. The number of events and the average number of events will also be provided in tabulations of TEAEs and serious TEAEs.

Adverse events with definite, probable, and possible relationship are considered related to study drug. Adverse events with unrelated and unlikely relationship are considered unrelated to study drug.

Histograms showing the frequency of the number of treatment-emergent AEs and SAEs in each treatment group will be included.

Exposure-adjusted event rates by treatment group and overall will be provided for participants with TEAEs, and with serious TEAEs. Each summary will present by decreasing incidence of PT per 100 subject years of exposure, calculated as (number of subjects with event/total patient-years). Years of exposure is either a) time from first treatment until start date of TEAE type or b) duration of exposure for subjects without a TEAE type. Poisson regression modeling will be used to derive rate ratios and 95% CIs for each SOC. Rate ratios will be compared using a two-sided 0.05 level test for Poisson count data.

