The number and percentage of subjects with TEAE with hospitalization required will be summarized by treatment group and overall, including the number of events, the average number of events and the exposure-adjusted event rates. Poisson regression modeling will be used to derive rate ratios and 95% CIs to compare hospitalization rates between treatment groups.

All adverse events occurring on study will be listed in subject data listings.

By-subject listings also will be provided for the following: subject deaths; serious adverse events; adverse events leading to withdrawal and adverse events with hospitalization required.

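### SAP 6.6.1 counts adverse events only to the last recorded visit, while the protocol collects them 7 or 14 days past participation, so new-onset late events reach the listings but not the summary tables

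*Protocol*

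**What the plan says.** - **Collection.** Protocol 8.2.4 records events from consent "until 7 (for non-serious AEs) or 14 days (for SAEs) after the last day of study participation".
- **Protocol analysis.** Protocol 9.4.4 codes and tabulates every reported AE and SAE by treatment group, with no treatment-emergent restriction.
- **SAP restriction.** SAP 6.6.1 states: "Analyses of adverse events will be performed for those events that are considered treatment emergent". It defines these as "any adverse event with onset after the administration of study medication through the end of the study", cross-referring to Section 5.2, and adds baseline events that worsen or are later judged drug-related within the same limit.
- **End date.** SAP 5.2 has no entry for the end of the study as such. Its End of Study Visit is "The last recorded visit date". Its On-Treatment Period is "The period from date of first dose of study drug through the Week 24 study visit".
- **Tables.** In SAP 6.6.1, the severity, relationship, withdrawal, histogram and exposure-adjusted rate summaries are specified for treatment-emergent events. So are serious events ("with any treatment-emergent serious adverse event (SAE) will be summarized by treatment group and overall") and hospitalizations ("The number and percentage of subjects with TEAE with hospitalization required will be summarized by treatment group and overall"). Deaths have a by-subject listing and no table of their own.
- **Recorded changes.** SAP Section 7 lists departures from the protocol analyses. The move from all reported events to treatment-emergent events is not among them.

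**The concern.** The protocol goes to the trouble of collecting events after participation ends, for longer when they are serious, but the SAP's counting rule stops earlier. An SAE that begins in that tail is in the database and in a listing, yet it enters no between-arm count or rate specified in 6.6.1.

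The rule matters most where the last recorded visit is well before the participant's last day in the study. After the Week 4 phone call, the only scheduled visits are at Weeks 12 and 24. If a fatal event begins between those visits, the last recorded visit can precede its onset by weeks. SAP 6.4.1 scores a death before the 24-week assessment as 0 m, so the same death would count in the primary efficacy analysis and be absent from the SAE tables. The same applies to an SAE that begins shortly after a participant withdraws from the study. The 14-day collection period is there to capture such events.

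**Working it through.** The plan gives no figure of its own on this point. The check compares two windows and counts days.

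**1. The windows**, for a participant whose last visit and last day of participation are both Day 168 (Protocol 8.1: Week 24 visit on Day 168 ± 7):

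| | Collected to (Protocol 8.2.4) | Counted to (SAP 6.6.1 with 5.2) | Gap |
|---|---|---|---|
| SAEs | 168 + 14 = Day 182 | Day 168 | 14 days |
| Non-serious AEs | 168 + 7 = Day 175 | Day 168 | 7 days |

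Using the On-Treatment Period as the anchor gives the same result for this participant, because it ends at the Week 24 visit.

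**2. Uncounted share of post-dose collection time** = k / (L + k), where L is the last visit day and k is 14 or 7.
- L = 168: SAEs 14/182 = 7.7%; non-serious AEs 7/175 = 4.0%.
- L = 161: 14/175 = 8.0%; 7/168 = 4.2%.
- L = 175: 14/189 = 7.4%; 7/182 = 3.8%.

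Collection starts at consent. Measured from consent on Day −14, the shares at L = 168 are 14/196 = 7.1% and 7/189 = 3.7%.

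**3. Follow-up time.** If all 80 participants complete on Day 168, uncounted SAE follow-up is 80 × 14 / 365.25 = 3.1 patient-years, against 80 × 168 / 365.25 = 36.8 patient-years to Day 168. The documents give no SAE rate. On an assumed 0.1 to 0.8 SAEs per patient-year, the tail would hold about 0.3 to 2.5 SAEs across both arms. This range is only as good as the assumed rate.

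**4. A death between visits.** Suppose the last recorded visit is Week 12 (Day 84), a fatal event begins after Day 84, and the participant dies on Day 120.
- SAP 6.6.1 with 5.2: the window closes on Day 84, so the event is not treatment-emergent and is not in the tables.
- SAP 6.4.1: 24-week 6MWD is set to 0 m.
- Up to 168 − 84 = 84 days of planned treatment lie outside the literal window.
- Adding 14 days to the last visit would reach only Day 84 + 14 = Day 98, still short of Day 120. The anchor must therefore be the last day of participation.

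**5. Time at risk.** For a participant without the event, SAP 6.6.1 uses duration of exposure, which SAP 6.3.4 ends at the last dose. The numerator window runs to the last visit. The two do not share an end date even now.

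**The case against.** The strongest reply is that this is an imprecise cross-reference. SAP 5.2 defines an End of Study Visit, not the end of the study, and equating them is an inference. That is fair. However, it is the only matching entry, and the other available anchor, the Week 24 visit, also omits the 7- and 14-day tail. A last recorded visit may be unscheduled or a withdrawal visit, so the cut-off can fall later than the last scheduled visit; this shortens the gap without removing it.

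Collecting beyond the treatment-emergent window and listing the remainder is also a defensible design. It would be acceptable if chosen openly, but Protocol 9.4.4 says otherwise and Section 7 records no such choice.

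Several stronger readings are tempting and are not supported:
- **That late SAEs and deaths vanish from the report.** The SAP 6.6.1 listings of deaths and SAEs carry no stated treatment-emergent limit. Protocol 8.2.5 also sends deaths to the DSMB within 48 hours, and DSMB reports cover all SAEs.
- **That a participant who withdraws while deteriorating and is later hospitalised or dies is not counted.** Inclusion depends on onset. An event that began before the last visit and later becomes serious remains treatment-emergent.
- **That everyone who stops early is affected.** SAP 5.4 follows those who stop drug to Week 24. The problem concerns study withdrawal, loss to follow-up and death.
- **That every safety table is affected.** The SAP's list of outputs (Section 10) is not in the text available here, so the statement covers only the summaries specified in 6.6.1. For hospitalizations the conflict is weaker, since Protocol 9.4.4 itself ends that summary at study termination.
- **That 7.7% of SAEs are lost.** The figure is a share of calendar time, not of events.

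**Conclusion.** The point holds as a conflict between the protocol's collection window and the SAP's counting window. Followed literally, the SAP leaves events with new onset after the last recorded visit out of the summary tables in 6.6.1.

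For on-time completers the gap is modest and has the same length in both arms, so nothing in the documents shows that it favours either arm. It can be much longer for participants who die or leave the study between visits. There the plan is also inconsistent with itself, scoring the death for efficacy while omitting it from the SAE tables.

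The conclusion assumes that the end of the study means the End of Study Visit and that the table programs follow the 6.6.1 text. The plan should be corrected, but the problem does not undermine the safety data, which are collected and listed.

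**What to change.** In SAP 6.6.1, define the treatment-emergent window as onset from first dose through 7 days (non-serious) or 14 days (serious, including fatal) after the last day of study participation, as in Protocol 8.2.4. State that this day is the date of completion, withdrawal, loss to follow-up or death, not the last recorded visit. Apply the same limit to worsening of baseline events. Use the same end date for time at risk in the exposure-adjusted rates, in place of duration of exposure to last dose for participants without the event. Add a table of all deaths by arm. Record the change from the protocol's all-reported-events tabulation in Section 7.

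The cost is a revised definition, a revised denominator, one added table and minor programming; the protocol already collects the events. The downside is a slightly different risk period for serious and non-serious events, which summaries that mix the two should footnote.
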